8.1. Efficacy Endpoint(s)

n/a.

8.2. Safety Endpoints

8.2.1. Vitals and ECGs

Temperature, supine vital signs will be summarized for the raw data and for the change from baseline data.

Triplicate 12-Lead ECG data will be summarized.

Incidence of QTc \geq 500 msec, or \geq 60 msec above baseline will be summarized.

8.2.2. Laboratory Data

Laboratory parameters will be summarized using summary tables on raw and change from baseline, and shift tables will also be generated.

8.2.3. Adverse Events

The incidence of adverse events will be summarized, for all adverse events (overall), for adverse events by relation to treatment, and adverse events by severity. The summaries will be prepared using Pfizer standards. The incidence of adverse events will be summarized by count of subject incidence. Any events observed following start of treatment or worsening in severity will be counted as treatment emergent.

The following parameters will be summarized:

- Incidence, severity and causal relationship of treatment emergent AEs (TEAEs).
- Incidence and severity of hypoglycemic events.
- Incidence of abnormal laboratory findings.

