- Weight measure in gown, undergarments and socks (or in comparable standard garments used by the CRU) while fasting and empty bladder. Height measured with wall-mounted stadiometer at screening only in stocking feet and carried forward.
- Vital signs: blood pressure, pulse, temperature. Only blood pressure should be collected in triplicate. On dosing days obtain at prior to dose and at 1, 2, and 4 hours after dosing.
- Screening labs include FSH in women only, TSH, C-peptide, HIV, hepatitis B surface antigen, hepatitis B core antibody, hepatitis C antibody.
- Subjects will continue to be monitored, at approximately 1-3 month intervals, for up to 9 months beyond the last scheduled visit, if necessary, for elevated glucagon levels and/or presence of anti-PF-06293620 antibodies.
- Samples for MMTT assessment should be collected prior to the MMTT (0 minutes/fasting) and after the start of the liquid meal at 15, 30, 60, 120, 180 and 240 minutes. Blood glucose, C-peptide, insulin, glucagon and GLP-1 will be measured at all timepoints.

- f. Fingersticks with glucometer measurements to be taken before breakfast (fasting), 2-hr post-breakfast, before lunch, 2-hr post-lunch, before dinner, 2-hr post-dinner, prior to snack (between 9 and 10 PM) and then at 0300 and before breakfast (fasting) the following days (Day 1, Day 9 and Day 65). Days 9 and 65 are done as outpatient, at home.
- g. PK: on dosing days, PK sample will be collected at hours 0 (predose), 1 and 4 hours post dose.
- h. Perform injection site assessment immediately after injection, 15 minutes, 30 minutes, 1 hour, and 2 hours post administration. Additional assessments should be performed as needed after the last assessment of 2 hrs post-dose on dosing days.
- i. Subject to be questioned about compliance with metformin.
- j. Triplicate ECG: All ECG will be submitted to Central ECG vendor for independent review. On dosing days, collect triplicate ECG prior to study drug administration (pre-dose) and 1, 2, and 4 hours after dosing.
- k. Fasting plasma glucose, glucagon and GLP-1 are not collected on days when MMTT are performed – these analytes will be captured as part of the MMTT Time 0/fasting timepoint.

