6.2.12. Day 85 (± 3)/Early Termination – SAD

The following procedures will be performed:

- Conduct limited physical exam of the skin, heart, lungs, abdomen and extremities by trained medical personnel at the investigator site.
- Assess temperature, supine pulse rate and triplicate supine blood pressure. Blood pressure will be the only vital sign collected in triplicate.
- Collect fasting weight and triplicate waist circumference.
- To measure waist circumference, use a spring-loaded tape measure, and starting at the top of the hip bone, bring it all the way around, level with the navel. Tape measure

should not be too tight and parallel with the floor. Instruct subject to not hold their breath. Measurement should not include navel.

- Collect triplicate 12-lead ECG.
- Collect fasting blood and urine samples for safety labs.
- Collect blood sample for fasting lipid profile.
- Collect blood sample for fructosamine and 1,5-anhydroglucitol.
- Collect blood samples for coagulation panel, amylase and lipase.
- Collect blood sample for HbA1c.
- Collect blood samples for FPG, fasting glucagon and fasting GLP-1.
- Collect blood sample for PK analysis.
- Collect blood sample for ADA analysis.
- Assess symptoms by spontaneous reporting of adverse events and by asking the subjects to respond to a non-leading question such as “How do you feel?”
- Record concomitant medications.
- Question subject on metformin compliance.
- Confirm contraception method.
- Schedule 1-3-month extended follow-up visit – site will be notified if visit will be required once data is available.

Note for extended follow-up: Subjects will continue to be monitored beyond the last scheduled visit, if necessary, for elevated glucagon levels and/or presence of anti-PF-06293620 antibodies (at approximately 1-3 month intervals) until their glucagon/ADA levels return to approximate baseline or establish a new steady-state level.

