7.2.13. Immunogenicity

Assays for the determination of human anti-PF-06293620 antibodies (ADA) will be performed. All samples that are positive in a screening assay will be confirmed for antibody specificity and further characterized for titer. Samples may also be analyzed in neutralization assays to determine whether or not they are neutralizing or non-neutralizing. Samples for ADA should be collected at times specified in the [Schedule of Activities](#) section of this protocol.

Following dosing, if a subject tests positive in the validated confirmatory ADA assay, this subject will be observed closely for signs and symptoms of hypersensitivity reactions including but not limited to changes in white blood cell count, platelet count and vital signs. Subjects found to have anti- PF-06293620 antibodies still present at the end of study will be requested to return to the clinic at 1-3 month intervals, for up to 9 months after the last scheduled visit, for blood collection to assess ADA until antibody levels return to baseline, or if ADA titers remains above baseline, no further visits are necessary if the titers have stabilized at consecutive visits and there are no signs and symptoms associated with the ADA lab result.

Blood samples (**4 mL**) to provide a minimum of 2 mL of serum for anti-PF-06293620 antibody analysis will be collected into appropriately labeled tubes. Additional instructions for sample collection, processing, storage and shipment will be provided in the laboratory manual.

Samples will be analyzed using a validated analytical method in compliance with Pfizer standard operating procedures.

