7.4.1. Pharmacodynamic Markers

7.4.1.1. Fasting plasma glucose, fasting plasma glucagon, fasting plasma GLP-1 and HbA1c

Blood samples for the assessment of FPG, fasting glucagon, fasting GLP-1 and HbA1c will be collected at times specified in the protocol. Fasting samples will be obtained following at least a 10 hour fast. Instructions for sample collection, processing, storage and shipment will be provided in the laboratory manual.

Subjects found to have elevated glucagon levels (ie, >3 X baseline) at the end of study will be requested to return to the clinic at 1-3 month intervals, for up to 9 months after the last scheduled visit, for blood collection to assess whether or not the glucagon levels return to approximate baseline (ie, ≤ 3 X baseline), or if glucagon remains above baseline, no further visits are necessary if the glucagon has stabilized at consecutive visits with no related adverse events. The 3 X baseline limit was set based on the variability of glucagon levels in the subjects that received placebo in the ongoing SAD study. In this study, of the six placebo subjects, glucagon maximum to minimum ratio varied from 1.5 to 3.5 within a subject.

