8. ADVERSE EVENT REPORTING

8.1. Adverse Events

Adverse events will be collected from the time a subject signs consent to the last visit. All observed or volunteered AEs regardless of treatment group or suspected causal relationship to the investigational product(s) will be reported as described in the following sections.

For all AEs, the investigator must pursue and obtain information adequate both to determine the outcome of the AE and to assess whether it meets the criteria for classification as a serious adverse event (SAE) requiring immediate notification to Pfizer or its designated representative. For all AEs, sufficient information should be obtained by the investigator to determine the causality of the AE. The investigator is required to assess causality.

Follow-up by the investigator may be required until the event or its sequelae resolve or stabilize at a level acceptable to the investigator, and Pfizer concurs with that assessment.

As part of ongoing safety reviews conducted by the Sponsor, any non-serious adverse event that is determined by the Sponsor to be serious will be reported by the Sponsor as a SAE. To assist in the determination of case seriousness further information may be requested from the investigator to provide clarity and understanding of the event in the context of the clinical study.

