8.2. Reporting Period

For SAEs, the active reporting period to Pfizer or its designated representative begins from the time that the subject provides informed consent, which is obtained prior to the subject's participation in the study, ie, prior to undergoing any study-related procedure and/or receiving investigational product, through and including 28 calendar days after the last administration of the investigational product. Serious adverse events occurring to a subject after the active reporting period has ended should be reported to the Sponsor if the investigator becomes aware of them; at a minimum, all serious events that the investigator

believe have at least a reasonable possibility of being related to investigational product are to be reported to the Sponsor.

Treatment emergent AEs (serious and non-serious) should be recorded on the CRF/DCT from the time the subject has taken at least one dose of study treatment through last subject visit.

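### Does the missing end day for treatment-emergent adverse events leave the TEAE comparison resting on unequal follow-up?

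*SAP*

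**What the plan says.** SAP 8.2.3 defines the count: "Any events observed following start of treatment or worsening in severity will be counted as treatment emergent". It reports subject incidence and refers to sponsor standards for the layout. SAP 10.2.2 adds a risk difference by treatment group without p values, and SAP 10.1 pools placebo and uses subjects, not person-time, as the denominator. TEAE incidence is a primary endpoint (Protocol 2.2.1).

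The protocol supplies the end of collection, but without a day number. Section 8.1: "Adverse events will be collected from the time a subject signs consent to the last visit". Section 8.2, for treatment-emergent events: "from the time the subject has taken at least one dose of study treatment through last subject visit". The one fixed limit in 8.2, "through and including 28 calendar days after the last administration of the investigational product", covers active reporting of serious events only.

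Some subjects return later. The MAD Schedule of Activities footnote provides for monitoring "for up to 9 months beyond the last scheduled visit, if necessary, for elevated glucagon levels and/or presence of anti-PF-06293620 antibodies". Protocol 6.2.12 continues SAD monitoring "until their glucagon/ADA levels return to approximate baseline or establish a new steady-state level". Protocol 6.3.29 adds MAD follow-up for liver enzymes that reached three times the upper limit of normal or more.

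**The concern.** Read alone, SAP 8.2.3 counts every event after the first dose, however late. Recall is selective: it depends on glucagon, antibody and liver findings after dosing, which may differ between active drug and placebo. The recall contacts are called visits, and adverse events bear on when they stop. For glucagon, "no further visits are necessary if the glucagon has stabilized at consecutive visits with no related adverse events". For antibodies, visits may end if "the titers have stabilized at consecutive visits and there are no signs and symptoms associated with the ADA lab result". So a recall visit could be taken as the last visit, and events noted there could enter the TEAE tables.

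Crude incidence has no adjustment for observation time, so a group with more recalled subjects would show more events even without a drug effect. SAP 5 also allows a MAD interim report before extended follow-up is complete, so one cohort's TEAE table could change between the interim and final reports.

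**Working it through.** The plan states no figure on this point, so there is none to reproduce. The check has two parts: which reading the text supports, and how large the effect could be on the other one.

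**1. Where does the text place the last visit?**

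| Place | What it shows |
|---|---|
| Protocol 6.3.29 | Glucagon and antibody recall runs up to 9 months after the last visit, so the last visit here is Day 169 |
| Protocol 3.1 | MAD follow-up is Days 86 to 169 |
| Schedules of Activities | The Adverse Event Monitoring rows stop at Day 85 (SAD) and Day 169 (MAD); the extension footnote is attached to the glucagon and antibody rows only |
| Protocol 7.2.13 and 7.4.1.1 | Recall concerns findings at the end of study, and its stated purpose is blood collection |
| SAP Appendix 1 | All analyses and summary tables follow the visit windows, which end at Day 100 (SAD) and Day 200 (MAD) |

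The first four rows point to Day 85 and Day 169. The fifth does not name adverse events. Read as literally as SAP 8.2.3, though, it limits the count as well:

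- SAD: a first recall one month after Day 85 ± 3 falls at Day 82 + 30 = 112 to Day 88 + 30 = 118, outside the last window (71 to 100).
- MAD: a first recall one month after Day 169 ± 5 falls at Day 164 + 30 = 194 to Day 174 + 30 = 204, partly inside the last window (161 to 200).

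**2. Longest possible windows if recall events counted**

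Nine months = 9 × 30.4375 = 274 days.

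- SAD: (85 + 274)/85 = 359/85 = 4.2.
- MAD: (169 + 274)/169 = 443/169 = 2.6.
- MAD with Appendix 1 as a cap: 200/169 = 1.18.

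These are maxima, since recall can stop early. The SAD figure borrows the 9-month limit from Protocol 7.2.13 and 7.4.1.1; section 6.2.12 states none.

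**3. Illustrative bias**

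Assumptions, none of them in the documents: constant event hazard, no drug effect, risk p = 0.30 over the scheduled period, a share f of 0.25 to 0.50 of active subjects recalled for the full extra time, and no placebo subject recalled. With k the window ratio, the spurious risk difference is f × [1 − (1 − p)^k − p].

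| Case | k | 1 − 0.70^k | Spurious risk difference, f = 0.25 to 0.50 |
|---|---|---|---|
| MAD, 9 months | 2.62 | 0.607 | 0.08 to 0.15 |
| SAD, 9 months | 4.22 | 0.778 | 0.12 to 0.24 |
| MAD, capped at Day 200 | 1.18 | 0.344 | 0.01 to 0.02 |
| Last visit = Day 85 or Day 169 | 1 | 0.300 | 0 |

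A simulation of the 9-month MAD case at f = 0.50 gave 0.155, and 0.001 with every subject cut off at Day 169. If equal shares of active and placebo subjects are recalled, the bias is zero. Placebo recall is possible: Protocol 7.4.1.1 reports within-subject maximum-to-minimum glucagon ratios of 1.5 to 3.5 on placebo, and the recall threshold is above 3 times baseline.

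**4. What one subject is worth**

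One added subject moves incidence by 1/6 = 16.7 points in a planned SAD active group, 1/8 = 12.5 at MAD 50 or 150 mg, and 1/16 = 6.25 at MAD 75 mg. The 6 mg/kg group already had 9 subjects at the May 2015 cut-off (Protocol 1.3.2), so there it is 1/9 = 11.1. These shifts are 1/n and apply to any event in a small cohort, so they are not evidence of bias. Overall incidence moves only if the subject had no earlier TEAE. A MAD subject recalled for ALT or AST will already have one, because Protocol 8.4 makes a value of three times the upper limit or more a reportable adverse event.

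**The case for a change.** The best case for the concern is that a primary safety count should not depend on how a programmer reads an undated term. Protocol 7.2.13, 7.4.1.1 and the schedule footnotes say *last scheduled visit*, which is not the term used for adverse event collection in 8.1 and 8.2. Protocol 13.1 ties the end of trial to the point at which no further evaluation is required, which could include recall. Appendix 1 assigns records to planned visits and was not written as an adverse event cut-off. One sentence would settle it.

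Some of this stands. The end day is not written down, and the terms vary. But Protocol 13.1 defines the end of trial, not adverse event collection. The wording about related events in 7.4.1.1 is a condition for stopping recall, and no procedure list for recall visits includes adverse event questioning. Unequal recall between arms is plausible, but no recall share is given, so neither direction nor size can be shown.

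A separate drafting point also stands. The stated length of extended follow-up differs: Protocol 6.2.12 gives no month limit, 6.3.29 gives none for liver enzymes, and 7.2.13, 7.4.1.1 and SAP 5 say up to 9 months. These passages must be reconciled, but they do not decide which adverse events are counted.

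**Conclusion.** The omission is real but calls for no change. It is an undefined term, and the surrounding text points analysts to Day 85 in SAD and Day 169 in MAD. On that reading subjects who complete have equal windows, the recall effect is zero, and the MAD TEAE table would not change because of recall between interim and final reports. The sponsor standards cited in SAP 8.2.3 may already fix the limit; they are not among the documents reviewed.

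The larger figures (windows of 2.6 and 4.2 times, a spurious MAD difference of 0.08 to 0.15) need three things together: recall events counted as treatment emergent, Appendix 1 not acting as a cap, and more recall on active drug than on placebo. The documents establish none of these. Early withdrawals still have shorter observation (three of 36 at the May 2015 cut-off), but an end day would not alter that. There are no hypothesis tests or p values, and escalation decisions use data from about the first 15 days, so they are untouched.

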8.2.4. Anti-Drug Antibody

For subjects developing anti-drug antibody, incidence of abnormal laboratory findings will be summarized. Additional PK/PD subgroup analyses may be performed.

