2.2. Endpoints

2.2.1. Primary Endpoints

- Incidence of dose limiting or intolerable treatment related adverse events (AEs).
- Incidence, severity and causal relationship of treatment emergent AEs (TEAEs).
- Incidence of anti-drug-antibodies.

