7.2.11. Subject Monitoring During Injection or Infusion

All subjects should be closely observed while receiving investigational product and monitoring for clinical signs of a systemic reaction will continue during the clinic confinement period for clinical signs of allergic reactions/hypersensitivity including but not limited to rash, flushing, urticaria, dyspnea, oral temperature $>38^{\circ}\text{C}$, symptomatic bronchospasm, allergy-related edema/angioedema, hypotension, and anaphylaxis.

In case of an allergic reaction/hypersensitivity, the Investigator should institute treatment measures deemed medically appropriate. Medications to treat hypersensitivity reactions should be available, such as IV saline, ibuprofen, and emergency drugs, including IV epinephrine, diphenhydramine, methylprednisolone, and albuterol. Any episode of infusion reaction must be captured in the source documents and on the Infusion Reaction Form in the Case Report Form.

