10.2.2.6. Injection Site Reaction Evaluation

The injection sites were assessed for erythema, induration, ecchymosis, injection site pain, injection site pruritus, or other observed characteristics after investigational product administration. Injection site reaction evaluation will be summarized by dose and reaction response over time.

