10.2.2.7. Other Safety Data – Screening and Other Special Purpose Data

The number and percentage of subject receiving study treatment administration will be summarized. The immunogenicity findings, for anti-drug PF-06293620) antibodies (ADA) will be summarized. All concomitant medication(s) as well as non-drug treatment(s) will be provided in the listings.

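### The only safety summary the SAP conditions on ADA status is laboratory abnormalities in ADA-positive subjects; hypersensitivity and injection-site reactions are not related to ADA status

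*SAP*

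**What the plan says.** Immunogenicity is part of the primary objective (Protocol 2.1.1), and "Incidence of anti-drug-antibodies" is a primary endpoint (Protocol 2.2.1).

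The protocol says what to look for in a subject who becomes positive. Under 7.2.13, after a positive confirmatory test, "this subject will be observed closely for signs and symptoms of hypersensitivity reactions", and white cell count, platelet count and vital signs are named among the signs. Section 7.2.11 requires monitoring for "clinical signs of allergic reactions/hypersensitivity including but not limited to rash, flushing, urticaria, dyspnea", and adds among others temperature above 38 °C and bronchospasm. It also requires a dedicated case report form for infusion reactions. Section 7.2.12 records injection-site reactions on their own form.

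The SAP deals with ADA in two places:

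- SAP 8.2.4: "For subjects developing anti-drug antibody, incidence of abnormal laboratory findings will be summarized", followed by "Additional PK/PD subgroup analyses may be performed".
- SAP 10.2.2.7: "The immunogenicity findings, for anti-drug PF-06293620) antibodies (ADA) will be summarized". No layout is given.

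The reactions are summarized elsewhere. SAP 10.2.2.6 says "Injection site reaction evaluation will be summarized by dose and reaction response over time". SAP 8.2.3 and 10.2.2 summarize treatment-emergent adverse events by incidence, severity, causality and treatment. SAP 10.1 presents all analyses by dose group, with placebo pooled.

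**The concern.** The SAP's one safety summary within ADA-positive subjects does not match the harm the protocol ties to ADA. Laboratory results cannot show rash, urticaria, bronchospasm, fever or an injection-site reaction. A percentage among ADA-positive subjects alone cannot be read without the same percentage among ADA-negative subjects on active drug. A count that ignores time also mixes findings that preceded ADA with findings that followed it.

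If reactions clustered in ADA-positive subjects, particularly at a second or third MAD dose given after seroconversion, no planned table would show it. A reader would have to match adverse event, injection-site and ADA listings by hand.

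**Working it through.** The plan gives no figure on this point, so the check is mainly a comparison of provisions.

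**1. Which summaries depend on ADA status**

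| Provision | Content | Split by ADA status? | Timed against ADA onset? |
|---|---|---|---|
| SAP 8.2.4, first sentence | Abnormal laboratory findings | ADA-positive only | No |
| SAP 8.2.4, second sentence | PK/PD subgroups, optional | Possibly | Not stated |
| SAP 10.2.2.7 | ADA findings themselves | Not applicable | Not stated |
| Protocol 9.5 | ADA incidence | Not applicable | Not stated |
| Protocol 9.3.2 | ADA effect on concentrations | Yes, PK only | No |
| SAP 8.2.3, 10.2.2 | Adverse events | No, by treatment | No |
| SAP 10.2.2.6 | Injection-site reactions | No, by dose | No |
| Infusion reactions | No summary named in the SAP | No | No |

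Only the first row is a committed safety summary conditioned on ADA. SAP Appendix 4 has no table shells yet, so no shell supplies the split.

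**2. Why timing matters**

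ADA samples are taken on Day -1, then Days 15, 29, 57 and 85 in SAD (Protocol 6.2.2, 6.2.9, 6.2.11, 6.2.12). In MAD they are taken on Day -1, then Days 15, 29, 57, 85, 113, 141 and 169 (Protocol 6.3.3 onward). Post-dose safety laboratory tests start earlier: Days 2, 5 and 8 in SAD, and Days 2 and 8 in MAD. Under SAP 8.2.4 an abnormality on Day 2 counts the same as one on Day 57 for a subject first positive on Day 15.

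Seroconversion is known only to lie between two samples. For that same subject the last negative sample is Day -1 and the first positive is Day 15, so the Day 1 dose falls inside the unknown interval. Counting everything after the last negative sample as post-ADA would put immediate Day 1 reactions on the wrong side.

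**3. Where the information lies**

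SAD gives one dose, with local or infusion assessments on Day 1 and later ones only as needed. Later ADA status therefore says little about those reactions. In MAD the Day 29 and Day 57 doses each have an ADA sample before dosing and injection-site assessment through 2 hours (Protocol 6.3.13, 6.3.16), so reactions can be read against ADA status at that dose.

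**4. Size**

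- SAD active subjects: 5 cohorts × 6 = 30 (SAP Table 1).
- MAD active subjects: 8 + 16 + 8 = 32 (SAP Table 2). Total 30 + 32 = 62.
- Assumed ADA rate: 5% to 30%, since the documents give none.
- SAD positives: 0.05 × 30 = 1.5 (about 2) to 0.30 × 30 = 9.
- MAD positives: 0.05 × 32 = 1.6 (about 2) to 0.30 × 32 = 9.6 (about 10).
- Exact two-sided 95% upper limit with zero events among n positives: 1 − 0.025^(1/n). For n = 2 it is 84%; n = 3, 71%; n = 6, 46%; n = 9, 34%; n = 10, 31%.

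Even with no reactions at all among positives, a true rate of at least 31% could not be excluded. Any split by ADA status can only describe.

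**The case against.** The strongest reply is that nothing required is missing. The primary endpoint is ADA incidence, and SAP 10.2.2.7 with Protocol 9.5 covers it. Neither document makes an association between ADA and safety an objective. The study is descriptive, all data are listed, and with a handful of positives, reading subjects one by one is ordinary phase 1 practice. The laboratory summary may also be laid out by parameter, which would show white cells and platelets, two of the signs Protocol 7.2.13 names. SAP 8.2.3 reports abnormal laboratory findings generally, with dose groups and pooled placebo as some reference.

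Most of this stands as a limit on how serious the point is. It does not remove it. The dose-group tables are not an ADA-negative comparator. The SAP already commits to a summary within ADA-positive subjects, so the question is only whether that summary can be interpreted.

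Three stronger readings are tempting, and the documents do not support them:

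- A reader might infer that SAP 8.2.4 is the only planned safety analysis of immunogenicity. It is not: ADA findings and incidence are also summarized.
- A reader might infer that the reactions appear in no summary. Injection-site reactions have their own summary, and hypersensitivity reported as an adverse event enters the adverse event tables.
- A reader might infer that the laboratory incidence would be near 100% because glucose is abnormal in this population. The SAP does not define an abnormal finding or say whether the count is by parameter, so this cannot be established.

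**Conclusion.** The point holds as a modest improvement. The SAP relates only laboratory abnormalities to ADA status, in positive subjects alone and without timing, while the protocol ties ADA to hypersensitivity. The reactions are reported, but not in relation to ADA. No primary estimate is invalidated, and the ADA incidence endpoint is answered.

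The gain is mainly in MAD, where dosing can follow seroconversion. It rests on an unknown number of positives: 2 to 9 in SAD and 2 to 10 in MAD under the assumed 5% to 30%. The documents give no reaction counts, so the size of any missed cluster cannot be stated.

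**What to change.** Replace the first sentence of SAP 8.2.4 with wording such as:

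> In active-treated subjects, separately for SAD and MAD, the number and percentage with hypersensitivity-type adverse events, infusion reactions (IV cohort), injection-site reactions, temperature above 38 °C, and white-cell or platelet abnormalities will be tabulated by ADA status: treatment-emergent positive or negative throughout. Subjects positive at baseline will be shown separately, and placebo for reference. For ADA-positive subjects, each event will be listed with its onset against the last negative and first positive sample dates, and classed as before the last negative, in the indeterminate interval, or after the first positive. Reactions around the first dose will be shown separately and not counted as after ADA. In MAD, reactions at the Day 29 and Day 57 doses will also be shown by ADA status at that dose.

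The SAP should list the adverse event terms that count as hypersensitivity-type and define an abnormal white-cell or platelet value.

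The cost is SAP wording and one or two descriptive tables from data already collected. SAP section 2 places finalization before database lock, so the change belongs there. The downside is small cells: the tables support no test and should carry none. No dose, schedule or clinical rule changes.
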